13.7 Communication to Health Authorities

The clinical trial protocol and its amendments and any applicable documentation (e.g. Investigator's Brochure, Subject Information and Informed Consent Form) will be submitted or notified to the Health Authorities.

14 TRIAL MANAGEMENT

14.1 Case Report Form Management

The Investigator or designee will be responsible for entering trial data in the eCRFs that will be provided by the Sponsor or its designee. It is the Investigator's responsibility to ensure the accuracy of the data entered in the eCRFs. Database lock will occur once quality control and quality assurance procedures (if applicable) have been completed.

14.2 Source Data and Subject Files

The Investigator must keep a subject file (medical file, original medical records) on paper or electronically for every subject included in the trial. This file will contain the available demographic and medical information for the subject, and should be as complete as possible.

In particular, the following data should be available in this file:

- Subject's full name
- Date of birth
- Gender
- Height
- Weight
- Relevant medical history and concomitant diseases
- Prior and concomitant therapies (including changes during the trial)
- Trial identification
- Date of subject's inclusion into the trial (i.e. date of informed consent)
- Subject identifier in the trial
- Dates of the subject's visits to the site
- Any medical examinations and clinical findings predefined in the clinical trial protocol
- All adverse events observed in the subject
- Date of subject's end of trial, and
- Date of and reason for early withdrawal of the subject from the trial or from treatment, if applicable.

It must be possible to identify each subject by using this subject file. Additionally, any other documents containing source data must be filed. This includes original printouts of data recorded or generated by automated instruments, PET-CT or CT scan images, ECG recordings, laboratory value listings, etc. Such documents must bear at least the subject identifier and the date when the procedure was performed. Information should be printed by the instrument used to perform the assessment or measurement, if possible. Information that cannot be printed by an automated instrument will be entered manually. Medical evaluation of such records should be documented as necessary and the documentation signed and dated by the Investigator.

The following information described in the eCRFs is regarded as the source data:

- Any investigator's comments
- Subject identifier
- Information on AE (e.g. seriousness, severity, outcome, and causality to the IP)
- Reason for providing concomitant medications and procedures (if applicable)
- Assessment of antitumor effect including tumor measurements

- Description about trial discontinuation

14.3 Investigator Site File and Archiving

The Investigator will be provided with an Investigator Site File upon initiation of the trial. This file will contain all documents necessary for the conduct of the trial and will be updated and completed throughout the trial. It must be available for review by the Monitor, and must be ready for audit by the Sponsor as well as for inspection by Health Authorities during and after the trial, and must be safely archived for at least 15 years (or per local requirements or as otherwise notified by the Sponsor) after the end of the trial. The documents to be thus archived include the Subject Identification List and the signed subject Informed Consent Forms. If archiving of the Investigator Site File is no longer possible at the site, the Investigator must notify the Sponsor.

All original subject files (medical records) must be stored at the site (hospital, research institute, or practice) for the longest possible time permitted by the applicable regulations, and/or according to ICH GCP guidelines or ordinance of GCP, whichever is longer. In any case, the Investigator should ensure that no destruction of medical records is performed without the written approval of the Sponsor.

14.4 Monitoring, Quality Assurance and Inspection by Health Authorities

This trial will be monitored in accordance with the ICH Note for Guidance on Good Clinical Practice (ICH Topic E6, 1996). The site Monitor will perform visits to the trial site at regular intervals.

The Sponsor, as well as Health Authorities, must be permitted to inspect all trial-related documents and other materials at the site, including the Investigator Site File, the completed CRFs, the IP(s), and the subjects' original medical records/files.

The clinical trial protocol, each step of the data captures procedure, and the handling of the data, including the final clinical trial report, will be subject to independent Quality Assurance activities. Audits may be conducted at any time during or after the trial to ensure the validity and integrity of the trial data.

14.5 Changes to the Clinical Trial Protocol

Changes to the clinical trial protocol will be documented in written protocol amendments. Major (substantial, significant) amendments will usually require submission to the Health Authorities and to the relevant IRB/IEC for approval or favorable opinion. In such cases, the amendment will be implemented only after approval or favorable opinion has been obtained.

Minor (non-substantial) protocol amendments, including administrative changes, will be filed by the Sponsor and by the Investigator at the clinical study site. They will be submitted to the relevant IRB/IEC or to Health Authorities only where requested by pertinent regulations.

Any amendment that could have an impact on the subject's agreement to participate in the trial requires the renewal of the subject's informed consent prior to implementation.

14.6 Clinical Trial Report

After completion of the trial, a clinical trial report according to ICH E3 will be generated by the Sponsor in consultation with the Principal Investigator.

14.7 Publication

The first publication will be a publication of the results of the analysis of the primary endpoint, that will include data from all trial sites. Lead Investigators will be identified based on accrual and Good Publication Practices and the decision to publish or present initial data will reside in the Sponsor in consultation with the lead Investigators. Publications or presentations prior to the generation of a final clinical study report will be clearly marked as preliminary reports.

Investigators will inform the Sponsor in advance about any subsequent plans to publish or present data from any portion of the trial. Any publications and presentations of the results (abstracts in journals or newspapers, oral presentations, etc.), either in whole or in part, by Investigators or their representatives will require a pre-submission review by the Sponsor. The Sponsor will not suppress or veto publications, but maintains the right to a reasonable delay of a publication in order to protect intellectual property rights.

1. INTRODUCTION

Tipifarnib is a selective nonpeptide inhibitor of farnesyl transferase (FTase), an enzyme that couples an isoprenyl group to a number of intracellular proteins. Prenylation is essential for membrane localization and functional activity of those proteins. By inhibiting farnesylation, a blockade of prenylated protein-mediated signal transduction pathway is accomplished, with attenuation of cell growth. Consequently, inhibition of signaling using highly potent and selective farnesyl transferase inhibitors was proposed as an effective therapeutic approach in multiple oncology indications.

Tipifarnib was the first specific inhibitor of FTase to enter clinical studies. The clinical development of tipifarnib began in 1997 and has consisted of over 70 clinical oncology and hematology studies. More details on tipifarnib are provided in the clinical study protocol as well as the Investigator's Brochure (Tipifarnib's Investigator's Brochure, Edition 16, 29 January 2021).

This statistical analysis plan (SAP) is intended to describe the planned analyses and presentation of study data to be included in the clinical study report (CSR) for Protocol KO-TIP-002. This SAP has been developed according to [REDACTED] Standard Operating Procedure (SOP) 700: Developing and Maintaining a Statistical Analysis Plan, and accordingly, this plan and any deviations from this plan must be finalized, approved, and placed on file before the study database is locked. As per ICH E9 guidelines [FDA 1998] the purpose of this statistical analysis plan (SAP) is to provide a more technical and comprehensive elaboration of the principal features of the analysis described in the protocol document and to include detailed procedures for executing the statistical analyses of the study endpoints and other collected data. This SAP is based on Amendment 7 of the Clinical Trial Protocol (dated 12 July 2019) and on the version of the electronic case report forms (eCRFs) current as of the date of this version of the SAP. If there are additional amendments to the protocol or eCRFs, this SAP will be updated, as appropriate.

2. STUDY OBJECTIVES

2.1. Primary Objective and Endpoint

Primary Objective: To determine the antitumor activity in terms of objective response rate (ORR) of tipifarnib in subjects with relapsed or refractory peripheral T-cell lymphoma (PTCL).

Primary Endpoint: Response assessments according to the Lugano Classification (Protocol Appendix II).

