Tumor assessments will be performed at screening, at the Day 22 visit (\pm 5 days) performed during Cycles 2, 4, 6 and once every approximately 12 weeks (cycles 9, 12, 15, etc.) thereafter, until disease progression. Additional tumor assessments may be conducted if deemed necessary by the Investigator. Subjects who discontinue tipifarnib treatment for reasons other than disease progression must continue tumor assessments until disease progression, withdrawal of subject's consent to study procedures or initiation of another anticancer therapy.

Determination of objective tumor response will be performed based on the Lugano Classification (Cheson 2014, [Appendix II: The Lugano Classification](#)) and/or measurable cutaneous disease according to the modified Severity Weighted Assessment Tool (mSWAT, Olsen 2011, [Appendix III: Modified Severity Weighted Assessment Tool](#)). Subjects who have experienced a complete response may be considered for transplantation. Information on this intervention and other subsequent anti-cancer therapies will be collected for these subjects.

Upon disease progression, subjects will be followed approximately every 12 weeks for survival until either death or 12 months after accrual of the last study subject, whichever occurs first. Information on subsequent anticancer therapy will be collected.

All subjects will be followed-up for safety during treatment and for approximately 30 additional days after treatment discontinuation (or until immediately before the administration of another anticancer treatment). Additional safety follow up may be conducted if unresolved toxicity is present at the End of Treatment visit.

NUMBER OF SUBJECTS PLANNED: Up to 70 study subjects.

SUBJECT SELECTION:

Inclusion Criteria

For inclusion of a subject in the study, all of the following inclusion criteria must be fulfilled:

1. Subject is at least 18 years of age.
2. Subject has a diagnosis of PTCL according to the most recent edition of the World Health Organization (WHO) Classification of Tumors of Hematopoietic or Lymphoid Tissues as follows:
 - a. Anaplastic large cell lymphoma (ALCL), ALK positive
 - b. ALCL, ALK negative
 - c. Angioimmunoblastic T-cell lymphoma (AITL)
 - d. Enteropathy-associated T-cell lymphoma
 - e. Extranodal natural killer (NK) T-cell lymphoma, nasal type
 - f. Hepatosplenic T-cell lymphoma

- g. Peripheral T-cell lymphoma, no otherwise specified (NOS)
- h. Subcutaneous panniculitis-like T-cell lymphoma

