6 OBJECTIVES

6.1 Primary Objectives and Endpoints

Primary Objective: To determine the antitumor activity in terms of objective response rate (ORR) of tipifarnib in subjects with relapsed or refractory peripheral T-cell lymphoma (PTCL).

Primary endpoint: Response assessments according to the Lugano Classification and/or mSWAT.

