7 SUBJECT SELECTION

7.1 Inclusion Criteria

For inclusion of a subject in the study, all of the following inclusion criteria must be fulfilled:

1. Subject is at least 18 years of age.
2. Subject has a diagnosis of PTCL according to the most recent edition of the World Health Organization (WHO) Classification of Tumors of Hematopoietic or Lymphoid Tissues as follows:
 - a. ALCL, ALK positive
 - b. ALCL, ALK negative
 - c. AITL

- d. Enteropathy-associated T-cell lymphoma
- e. Extranodal natural killer (NK) T-cell lymphoma, nasal type
- f. Hepatosplenic T-cell lymphoma
- g. PTCL, NOS
- h. Subcutaneous panniculitis-like T-cell lymphoma

For enrollment into the AITL expansion cohort, subjects must have the diagnosis of AITL, nodal PTCL with T-follicular helper phenotype or follicular PTCL.

For enrollment into the CXCL12+ PTCL expansion cohort, subjects must have the diagnosis of PTCL (a – h subtypes listed above, except AITL), consent to provide buccal swabs for CXCL12 SNP testing, and be found to be CXCL12+ based on testing by a Sponsor approved methodology. Once (if) the AITL cohort has completed accrual, subjects with AITL histology and CXCL12+ status may be enrolled in the CXCL12+ PTCL expansion cohort.

- 3. Subject has relapsed or are refractory to at least 1 prior systemic cytotoxic therapy. Subjects must have received conventional therapy as a prior therapy.
- 4. Subject has consented to provide at least 6 unstained tumor slides (10 preferred) or an FFPE block for biomarker testing. Tumor tissue may be obtained from prior archival diagnostic biopsies. If the site is unable to confirm during screening that sufficient archival biopsy is available, the subject must consent to a pretreatment biopsy for inclusion in this study.
- 5. Subject has measurable disease according to the Lugano Classification and/or mSWAT.
- 6. At least 2 weeks since the last systemic therapy regimen prior to enrollment. Subjects must have recovered to NCI CTCAE v. 4.03 < Grade 2 from all acute toxicities (excluding Grade 2 toxicities that are not considered a safety risk by the Sponsor and Investigator) or toxicity must be deemed irreversible by the Investigator.
- 7. At least 2 weeks since last radiotherapy if radiation was localized to the only site of measurable disease, unless there is documentation of disease progression of the irradiated site. Subjects must have recovered from all acute toxicities from radiotherapy.
- 8. ECOG performance status of 0-2 ([Appendix 1](#)).

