8. EFFICACY ANALYSIS

8.1. Primary Efficacy Analysis

The primary endpoint will be based on response assessments according to the Lugano Classification (Protocol Appendix II). Either complete or partial responses can contribute to an objective response. The objective response rate, \hat{p}_{ORR} , will be estimated as a ratio of subjects with an objective response to the number of subjects (N) in the FAS data set.

The 95% Confidence Interval for ORR will be calculated using Wilson³ approximation.

If $\hat{P}_{ORR} \times N \leq 4$, the exact Clopper-Pearson⁴ method will be used for interval estimation.

Null hypothesis $H_0: \hat{P}_{ORR} = 10\%$ versus $H_A: \hat{P}_{ORR} > 10\%$ will be tested at $\alpha = 0.05$ significance level using a two-sided binomial test. The choice of test statistics will be driven by the method used for interval estimation.

The ORR analysis will be presented by means of a summary table and visualization. A summary table of the objective response rates will be provided for the primary efficacy endpoint for both the FAS [REDACTED] populations. [REDACTED]

The ORR will also be analyzed by study population subgroups (part of the secondary analysis) which are based on the genetic sub-types.

Sensitivity analysis, as part of the exploratory analysis, may also include analysis using different statistical approaches (different methods for interval estimation variants of normal approximation, Agresti-Coull, Pearson-Clopper, etc.), one-sided confidence intervals, test statistics, or a modelling framework). Exploratory analyses may also include a logistic regression modeling framework to evaluate the effect of genetic sub-types and other covariates on ORR.

Additional sensitivity and subgroup analysis, as part of exploratory analysis, may be conducted as deemed appropriate.

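### The SAP narrows the primary endpoint from Lugano and/or mSWAT to Lugano alone, does not list the change, and gives no rule for subjects enrolled on cutaneous disease only

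*SAP*

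**What the plan says.** **Protocol, Amendment 7.** The Synopsis explains what mSWAT adds: response is judged by Lugano "and/or measurable cutaneous disease according to the modified Severity Weighted Assessment Tool". The same pair of criteria appears wherever the protocol defines disease or outcome:
- Section 7.1, criterion 5: "Subject has measurable disease according to the Lugano Classification and/or mSWAT".
- Section 6.1: "Primary endpoint: Response assessments according to the Lugano Classification and/or mSWAT".
- Section 6.2, for PFS and DOR.
- Section 8.1, for the investigator's determination of response.
- Section 10.1, for the lesions to be assessed.
- Section 12.2.1, for disease progression.

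**SAP.** Section 1 says the plan is based on Amendment 7. Section 2.1 then reads "Response assessments according to the Lugano Classification (Protocol Appendix II", and Section 8.1 reads "The primary endpoint will be based on response assessments according to the Lugano Classification (Protocol Appendix II". Section 2.2 uses Lugano for DOR. Section 3.1 repeats the protocol's sentence on response determination without its mSWAT part. Section 8.2 takes progression from the primary endpoint assessment, so PFS and DOR inherit the narrowing. mSWAT does not appear in the SAP text supplied, including its abbreviation list.

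**SAP Section 14** lists four changes from the protocol: no separate ORR by histology, an added exploratory efficacy analysis, added adverse event summaries, and no laboratory change or shift analysis. The endpoint criterion is not among them.

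**The concern.** Entry and analysis no longer match. The and/or in criterion 5 lets a subject in on skin disease alone. Under the SAP, response is read by a criterion on which that subject may have nothing measurable, and no rule says what happens next.

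Three things are at stake:
- **The ORR.** If such subjects stay in the denominator and cannot respond, the estimate is too low. If they leave the FAS, the denominator changes, and in a direction that depends on how they fared.
- **PFS and DOR.** Progression in skin by mSWAT is an event under the protocol and has no stated role in the SAP. This also touches subjects with both nodal and skin disease.
- **Transparency.** A reader of Section 14 would conclude that the primary endpoint is unchanged. In an open-label, investigator-assessed trial, the handling of these subjects should be fixed before the outcomes are analysed.

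**Working it through.** **1. Side by side**

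| Item | Protocol | SAP |
|---|---|---|
| Measurable disease at entry | Lugano and/or mSWAT (7.1) | not restated |
| Primary endpoint | Lugano and/or mSWAT (6.1) | Lugano (2.1, 8.1) |
| Response determination | Lugano and/or mSWAT (8.1) | Lugano (3.1) |
| DOR | Lugano and/or mSWAT (6.2, 12.2.1) | Lugano (2.2) |
| Progression for PFS | Lugano and/or mSWAT (6.2, 12.2.1) | follows the primary endpoint assessment (8.2) |
| Listed as a change | not applicable | no (14) |

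The SAP sentences are complete and point to Protocol Appendix II. mSWAT is in Appendix III, so this is not a gap left by redaction or text extraction.

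**2. Which subjects are affected.** The protocol excludes primary cutaneous ALCL and mycosis fungoides/Sezary syndrome (7.2), which keeps the number low. It admits subcutaneous panniculitis-like T-cell lymphoma and does not bar skin involvement in other subtypes (7.1). The group is small by design but not empty by design.

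**3. How they would be counted.** SAP Section 5 requires one post-dose disease response assessment for the FAS and does not name the criterion. Section 6.4 imputes nothing. Both routes, non-responder or outside the FAS, fit the text.

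**4. The plan's own figures.** SAP Section 4 gives about 80% power at a true ORR of 30% with N = 65. The exact binomial calculation requires at least 2 of 11, then at least 4 of 18, then at least 12 of 65, and gives 0.797, which agrees. No stated figure depends on mSWAT, so the arithmetic below only sizes the effect.

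**5. Effect on the ORR at N = 65**
- One responder counted as a non-responder: 1/65 = 1.5 points. Two: 2/65 = 3.1 points.
- Expected ORR at a true 30% when k subjects stay in the denominator and can never respond is 0.30 × (65 − k)/65. This is 29.5% for k = 1, 29.1% for k = 2 and 28.6% for k = 3. The values of k are assumptions.
- If the subject leaves the FAS instead, take 12 of 65 (18.5%) as an example. Removing a responder gives 11/64 = 17.2%, down 1.3 points. Removing a non-responder gives 12/64 = 18.75%, up 0.3 points.
- The SAP also reports ORR by subgroup. In a cohort of 12, one lost responder is 1/12 = 8.3 points.

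**6. Effect on the test against 10%**
- z = (x/N − 0.10)/√(0.09/N). With N = 65, x = 11 gives 1.86 and x = 12 gives 2.27, so the rejection count is 12.
- Responses already reported in the protocol: 5 in the AITL cohort and 5 in the CXCL12+ cohort (12.4), plus 2 early AITL partial responses (8.1). 5 + 5 + 2 = 12.
- Cross-check: Section 5.2 reports 9 responses among all AITL subjects (5 CR, 4 PR). This equals 5 in the AITL cohort, 2 AITL responders in the CXCL12+ cohort and 2 early.
- Even with no further response, 12 gives z = 2.27 at N = 65 and 1.99 at N = 70. The extension of up to 20 AITL and related subjects is still to be added.

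**The case against.** The strongest reply is that this may be a difference in wording with no subject behind it. No passage reports anyone enrolled on skin disease alone, the main cutaneous entities are excluded, and up to 32 of the 70 places (12 + 20) are in the AITL cohort. That stands as a limit on size. It does not remove an unlisted narrowing of the primary endpoint.

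A reader might infer that a skin-only subject cannot be scored a responder at all. The documents do not support that. Protocol Appendix II was not available for this review, and imaging is scheduled for every subject, so a Lugano reading may exist even where skin is the only measurable disease. What can be said is that the SAP states no route. Likewise, exclusion from the FAS is only a possibility, because a post-dose scan could satisfy the definition.

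A reader might also infer that one lost responder could overturn the test, since 11 of 65 misses and 12 rejects. The chance of exactly 11 of 65 is 12.0%, 10.7% and 3.8% at true rates of 15%, 20% and 25%, but 0.7% at the design rate of 30%. More to the point, the protocol already implies at least 12 responses, with more AITL subjects to come. It does not say which criterion scored each response, so the risk is remote rather than zero.

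Finally, it is not shown that mSWAT scores were recorded. Section 10.1 calls for lesion assessment by Lugano and/or mSWAT, but Table 1 has no skin-scoring row and its tumor assessment footnote covers only imaging and bone marrow. This point stands and shapes the fix.

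**Conclusion.** The contradiction holds. The SAP, written for Amendment 7, replaces the protocol's primary endpoint criterion with a narrower one, carries the change into DOR and PFS, and does not declare it. Subjects whom the protocol admits on cutaneous disease alone are left without a scoring rule.

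The size is 1.5 points of ORR per lost responder at N = 65 and 8.3 points in a cohort of 12, multiplied by a number of subjects that is not given and may be zero. The consequence is for the estimate, its interval and the definition of progression. It is unlikely to change the conclusion against 10%.

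This rests on two assumptions: that some subjects have no Lugano-measurable disease, and that Lugano as set out in Appendix II would not credit their skin response. The discrepancy itself and its absence from Section 14 need neither.

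**What to change.** Restore the protocol's criterion, Lugano and/or mSWAT, in SAP Sections 2.1, 2.2, 3.1, 8.1 and 8.2. State that mSWAT decides response where it is the only measurable disease, and how the two criteria combine when both apply. Show the Lugano-only ORR as a sensitivity analysis.

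If Lugano alone is intended, or mSWAT scores were not captured in the eCRF, declare it in Section 14 as a change to the primary endpoint with the reason. Report how many subjects lacked Lugano-measurable disease and how they are counted in the FAS. If the number is zero, one sentence settles the effect on the ORR.

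Either route should be completed before database lock. If mSWAT was recorded, the cost is SAP wording and one extra analysis. If it was not, the second route is still a text change plus a count.
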